**CONFIDENTIAL**

Date:  
Version:  
Status:  
Page:

30 November 2020  
5.0  
Final  
35 of 105

**Novo Nordisk**

in a diabetic subject is poor compliance with treatment regimens or an atypical course of the disease. The upper HbA1c limit is also expected to select a population that can achieve adequate basal insulin coverage in the 8-week run-in basal insulin titration period. Subjects in relative good glycaemic control defined as HbA1c <7.5 % may not significantly benefit from this trial and hence the lower cut-off value has been chosen.

Protocol  
Trial ID: NN1218-4357  
UTN: U1111-1197-8289

**CONFIDENTIAL**

Date:  
Version:  
Status:  
Page:

30 November 2020  
5.0  
Final  
36 of 105

**Novo Nordisk**

## 7 Milestones

Planned duration of recruitment period (i.e. First Subject First Visit (FSFV) to Last Subject First Visit (LSFV)) is 18 months.

End of trial is defined as Last Subject Last Visit (LSLV).

### **Recruitment:**

The screening and randomisation rate will be followed closely via the interactive web response system (IWRS) in order to estimate when to stop screening. The ratio of randomised subjects with T1DM (minimum 20%) and subjects with T2DM (maximum 80%) will be controlled by the IWRS. All investigators will be notified immediately when the recruitment period ends or when the maximum number of subjects with T2DM has been reached, after which no further subjects may be screened and the IWRS will be closed for further screening. Subjects screened and found eligible can be randomised.

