## 6 Trial population

### 6.1 Number of subjects

Number of subjects planned to be screened: 505

Number of subjects planned to be included in the run-in period: 353

Number of subjects planned to be randomised: 300

At least 20% of the subjects randomised are expected to be subjects with T1DM.

A screening failure rate of approximately 30% and a run-in failure rate of approximately 15% are anticipated for this trial.

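### In Protocol Section 7 the T2DM cap closes screening to T1DM as well, so as written it cannot protect the 20% T1DM minimum when T1DM lags behind T2DM

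*Protocol*

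**What the plan says.** Protocol Section 7 (Milestones, Recruitment) sets the quota and names the system that enforces it: "The ratio of randomised subjects with T1DM (minimum 20%) and subjects with T2DM (maximum 80%) will be controlled by the IWRS".

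The next sentence gives two triggers, the end of recruitment and the T2DM maximum. The second reads: "when the maximum number of subjects with T2DM has been reached, after which no further subjects may be screened". One consequence applies to both: "no further subjects may be screened and the IWRS will be closed for further screening". For subjects already in progress it adds: "Subjects screened and found eligible can be randomised". Some forecasting is also intended: "The screening and randomisation rate will be followed closely via the interactive web response system (IWRS) in order to estimate when to stop screening".

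Protocol Section 6.1 words the quota more softly: "At least 20% of the subjects randomised are expected to be subjects with T1DM". The sample-size text assumes a T1DM share of 20% (Protocol Section 17.1) or at least 20% (SAP Section 5). Protocol Sections 10 and 11 list the IWRS functions and stratify randomisation by diabetes type. Neither keeps T1DM screening open after the T2DM maximum. The SAP contains no recruitment rule.

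**The concern.** A cap on the faster-recruiting group protects a minimum in the slower one only if the slower group stays open after the cap is reached. Section 7 closes both at once. That fixes the mix at whatever it happens to be, and it does so in the one situation where the minimum needs protection.

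At stake are the stated T1DM share and the precision of the separate T1DM treatment difference planned in Protocol Section 17.3 (Additional analysis) and SAP Section 4.3.3. The trial is also meant to support registration in both types (Protocol Section 3.2). The separate T1DM estimate has no margin and no test attached, so no planned conclusion hangs on it.

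**Working it through.** **Inputs from the documents.** 300 randomised, screening failure 30%, run-in failure 15% (Section 6.1); 20% / 80% limits (Section 7); 18-month recruitment (Section 7); about 2 weeks of screening and 8 of run-in (Section 5.1); SD 1.2, margin 0.4, true difference -0.02, one-sided 2.5%, 10% dropout (Section 17.1).

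**Assumptions of this check.** Even accrual; 18 months = 78 weeks; 10 weeks from screening to randomisation; the accrual patterns below. None of the patterns is given in the documents.

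**Plan's own figures.** With 270 completers, SE = 1.2 × √(4/270) = 0.146 and the noncentrality is (0.4 + 0.02)/0.146 = 2.88. The noncentral t gives power 81.7%, as stated. 300/0.85 = 353 and 353/0.70 = 504, against 353 and 505 stated. The limits imply 0.80 × 300 = 240 T2DM and 60 T1DM.

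**What closing both types does.** If T1DM is a share p of accrual, T1DM at the cap is 240p/(1−p) and its share of the total is p. For p = 5%, 10%, 15% and 20% this gives 12.6, 26.7, 42.4 and 60 T1DM subjects. The 20% is met only if T1DM was already at 20%.

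**T1DM on plan (60 in 78 weeks), T2DM faster by a factor f = 1.25 / 1.5.** The T1DM half-width is t(0.975, n−2) × 1.2 × √(4/n), with n = 0.9 × T1DM.

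*Cap counts expected randomisations*
- Closing week: 78/f = 62.4 / 52.0.
- As written: T1DM 60/f = 48 / 40; N = 288 / 280; share 16.7% / 14.3%; half-width 0.74 / 0.81; pooled power 80.1% / 79.0%.
- T2DM-only closure: T1DM reaches 60 by week 78; N = 300; share 20%; half-width 0.66; power 81.7%.

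*Cap counts randomised subjects, and those in progress are randomised as Section 7 allows*
- Closing week: 78/f + 10 = 72.4 / 62.0. This falls inside the 78-week window only if f ≥ 78/68 = 1.15.
- As written: T1DM = week × 60/78 = 55.7 / 47.7; T2DM = week × f × 240/78 = 278.5 / 286.2; N about 334; share 16.7% / 14.3%; half-width 0.68 / 0.74.
- T2DM-only closure, T1DM open until the 300th randomisation at week 10 + 300/(60/78 + f × 240/78) = 75.0 / 65.7: T1DM 57.7 / 50.5; N about 336 / 337; share 17.2% / 15.0%; half-width 0.67 / 0.72.

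**T1DM itself slow: total rate as planned (300/78 = 3.846 per week), T1DM share s = 10% / 15%.**
- Cap on expected randomisations: week 240/((1−s) × 3.846) = 69.3 / 73.4. T1DM 26.7 / 42.4 as written, against 300s = 30 / 45 if kept open to week 78. The rule costs 3.3 / 2.6 subjects.
- Pooled power is 77.0% / 79.4% as written and 77.6% / 79.7% with T1DM kept open. The rule accounts for about half a point or less.
- Cap on randomised subjects: week 79.3 / 83.4, after the window, so the rule never acts.

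**The case against.** The strongest reply is that this is a slip of wording. The sentence before says the IWRS controls the ratio, and a separate T2DM trigger has little purpose if it simply ends recruitment. The sponsor probably meant that no further T2DM subjects may be screened. That is a fair reading of intent, but the operative text says otherwise and nothing elsewhere in the protocol corrects it. How the IWRS was actually configured cannot be seen from these documents.

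The second reply is that the limits are set on randomised subjects, so the natural count is of randomised subjects. On that count the fix adds only 2 to 3 T1DM subjects, or the rule never acts at all. This stands, and it is the main reason the point is minor. The larger benefit needs a forecast count together with T1DM on plan and T2DM well ahead of plan.

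Three stronger readings are tempting and should not be made:
- *That the rule threatens the primary analysis.* A reader might set the 77.0% / 79.4% of the slow-T1DM pattern against the planned 81.7%. Nearly all of that gap comes from slow T1DM accrual and would remain after the fix. On the randomised count with T2DM ahead of plan, N is about 334 and pooled power, by the same calculation, is about 86%.
- *That the plan is silent on T2DM subjects in progress when the cap is reached.* It is not: "Subjects screened and found eligible can be randomised", without limit by type. The same sentence lets T2DM pass 240.
- *That 20% is a hard requirement throughout.* Section 7 calls it a minimum, but Section 6.1 only expects it.

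**Conclusion.** The point holds, as a minor correction. The closing rule in Section 7 is wrong as written: it stops T1DM screening when T1DM lags, and so cannot secure the minimum that the preceding sentence says the IWRS controls.

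The consequence is conditional. It is material (12 / 20 T1DM subjects lost) only if the cap counts expected randomisations while T1DM is on plan and T2DM runs 25% / 50% ahead. Otherwise the rule costs about 2 to 3 T1DM subjects, or nothing. Pooled power and the non-inferiority conclusion are essentially unaffected. The gain from correcting it is a better chance of meeting the stated T1DM share and a somewhat more precise separate T1DM estimate. All sizes rest on even accrual, a 10-week lag and assumed recruitment rates; the defect in the rule itself does not.

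**What to change.** Reword the Recruitment text in Section 7 so that reaching the T2DM maximum closes screening in the IWRS for subjects with T2DM only. T1DM screening then stays open until the planned number of subjects is randomised or the 18-month recruitment period ends, whichever comes first.

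The cost is one or two sentences and a closing step by diabetes type. The IWRS already uses diabetes type to stratify randomisation (Section 11); it would need it at the screening session as well. Recruitment is not prolonged beyond the planned period.

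Two limits remain. The rewording cannot guarantee 20% if T1DM accrual is slow. On a randomised count with in-progress subjects randomised, the total would pass 300 (about 336 in the patterns above), but the current wording gives about 334 there already.

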### **Trial registration:**

Information of the trial will be disclosed at clinicaltrials.gov, chinadrugtrials.org.cn and novonordisk-trials.com. According to the Novo Nordisk Code of Conduct for Clinical Trial Disclosure, it will also be disclosed according to other applicable requirements such as those of the International Committee of Medical Journal Editors (ICMJE), the Food and Drug Administration Amendment Act (FDAAA) European Commission Requirements and other relevant recommendations or regulations including requirements by the China Food and Drug administration (CFDA). If a subject requests to be included in the trial via the Novo Nordisk e-mail contact at these web sites, Novo Nordisk may disclose the investigator's contact details to the subject. As a result of increasing requirements for transparency, some countries require public disclosure of investigator names and their affiliations.

The Primary Completion Date (PCD) is the last assessment of the primary endpoint, and is for this trial Last Subject First Treatment + 16 weeks corresponding to V26. If the last subject is withdrawn/dropout early the PCD is considered the date when the last subject would have completed V26. The PCD determines the deadline for the results disclosure at clinicaltrials.gov according to FDAAA.

## 8 Methods and assessments

The following sections describe the assessments and procedures. These are also included in the flow chart (see Section 2) along with their timing.

### 8.1 Visit procedures

#### 8.1.1 Screening (V1)

Informed consent must be obtained before any trial related activity, see Section 18.2.

All subjects must be provided with a copy of their own signed and dated informed consent form.

Subjects will continue on their current diabetes treatment until start of the run-in period (V2) and they will not be supplied with any trial products until then.

At screening, subjects will be provided with a card stating that they are participating in a trial and giving contact address(es) and telephone number(s) of relevant trial site staff. Subjects should be instructed to return the card to the investigator at the last trial visit or to destroy the card after the last visit.

A screening session must be performed in the IWRS, see Section 10. Each subject will be assigned a unique 6-digit subject number which will remain the same throughout the trial. The investigator must keep a subject screening log, a subject identification code list and a subject enrolment log. Only subjects who have signed the informed consent form should be included on the logs. The subject screening log and subject enrolment log may be combined in one log.

Inclusion or exclusion criteria should not be answered “Yes” or “No” in the electronic case report form (eCRF) before source data is available. For central laboratory results, ECG and eye examination evaluations “Result pending” can be answered. Answers to these criteria should be changed to “Yes” or “No” when results and/or evaluations are available.

The investigator is required to make a reasonable effort to obtain necessary additional information from external sources e.g. primary physician and other hospitals/departments to document the subjects’ eligibility. Unless otherwise mentioned, all concomitant illness and medical history related to the inclusion and exclusion criteria are based on source documents such as the subject's medical record. It is the responsibility of the investigator to have sufficient evidence to ensure eligibility.

#### Screening failures

For screening failures, the end of trial form in the eCRF must be completed with the reason for not continuing in the trial. A minimal set of screen failure information is required to ensure transparent reporting of screen failure subjects to meet requirements from regulatory authorities. Minimal information includes date of informed consent, demography, screen failure details, eligibility criteria, and any SAE (serious adverse events). SAEs from screening failures

Protocol  
Trial ID: NN1218-4357  
UTN: U1111-1197-8289

**CONFIDENTIAL**

Date:  
Version:  
Status:  
Page:

30 November 2020  
5.0  
Final  
38 of 105

**Novo Nordisk**

must be transcribed by the investigator into the eCRF. Follow-up on SAEs must be carried out according to Section 12.

A screening failure session must be made in the IWRS and the case book must be signed.

Re-screening is not allowed if the subject has failed one of the inclusion, exclusion or randomisation criteria, this includes re-sampling if the subject has failed one of the inclusion, exclusion or randomisation criteria related to laboratory parameters.

### **8.1.2 Run-in (V2)**

If the subject is found eligible to continue in the trial the subject will enter an 8-week run-in period. V2 can take place as soon as the subject has been found eligible and must take place no later than 17 days after V1.

At start of the run-in period (V2), the subject will receive the trial products; basal insulin (insulin-degludec) and bolus insulin (NovoRapid®) (Section 9). The subject must be trained in how to handle the insulin pen-injectors (Section 8.6.1). Training may be repeated during the trial. Date of first trial products must be recorded in the eCRF.

A run-in dispensing session must be performed in the IWRS. A drug accountability session confirming dispensing of allocated trial products should also be performed.

The BG meter, BG meter test strips and a diary must be provided to the subject at V2. Subjects must be trained in use of the BG meter and completion of the diary.

#### **Run-in failures**

Subjects fulfilling any of the run-in period exclusion criteria, not fulfilling the randomisation criterion or withdrawing from trial during the run-in period are considered as run-in failures. Consequently, a run-in failure session must be made in the IWRS and a run-in failure form must be completed in the eCRF together with the reason for not continuing in the trial. The last date of trial product must be captured in the eCRF. No follow-up visit should take place and no additional assessments are needed.

SAEs and non-serious AEs from run-in failures must be recorded by the investigator in the eCRF. Follow-up of AEs must be carried out according to Section 12.3.

When data has been monitored and queries have been resolved the casebook must be signed in the eCRF.

Protocol  
Trial ID: NN1218-4357  
UTN: U1111-1197-8289

CONFIDENTIAL

Date:  
Version:  
Status:  
Page:

30 November 2020  
5.0  
Final  
39 of 105

Novo Nordisk

### 8.1.3 Randomisation (V10)

If the subject meets the randomisation criterion as measured at V9, the subject will at V10 be randomised into one of the two treatment arms using an IWRS randomisation session. A drug accountability session confirming dispensing of allocated trial products should also be performed.

First date of the randomised trial product (bolus insulin) must be recorded in the eCRF.

The subject must attend the randomisation visit fasting. For definition of fasting, please see Section [8.1.5](#).

### 8.1.4 Phone contacts

Before any phone contact, both the investigator and subject should agree on the timing and direction of the call. The investigator remains responsible for ensuring that the phone contacts occur even if it is agreed that the subject should call the site. A phone contact may be converted to a site visit if needed.

### 8.1.5 Fasting visits

The subject must attend the visits specified in the flowchart (Section [2](#)) in a fasting condition. Fasting is defined as at least eight hours without drink or food intake prior to the visit except for water.

Insulin dosing (including basal insulin) and medication which should be taken with or after a meal should be withheld until blood sampling has been performed. If a subject attends the visit non-fasting, then the subject's blood samples, meal test and body weight measurement should be rescheduled within the visit window and at V10 before randomisation to trial product.

### 8.1.6 Rescheduled visits

The date of the rescheduled assessment in the eCRF should reflect the actual date of the rescheduled assessment (i.e. the actual visit date will differ from the assessment date under the same visit).

### 8.1.7 End of treatment (V26)

At end of treatment (V26) trial products must be discontinued and an IWRS completion session must be performed. Last date on the basal and bolus trial insulins must be recorded in eCRF.

The subject should be switched to a suitable marketed product(s) at the discretion of the investigator.

### 8.1.8 Follow-up period

Protocol  
Trial ID: NN1218-4357  
UTN: U1111-1197-8289

**CONFIDENTIAL**

Date:  
Version:  
Status:  
Page:

30 November 2020  
5.0  
Final  
40 of 105

**Novo Nordisk**

The follow-up visit 1 (V27) is a site visit and should take place 7-12 days after the end of treatment visit. Follow-up contact 2 (P28) is a phone contact and should take place 30-35 days after the end of treatment visit.

### **Follow-up visit 1**

The following data will be collected:

- AEs
- Concomitant medication
- Current diabetes medication
- Hypoglycaemic episodes
- Additional information on injection site reactions (see Section [8.4.1.2](#))

### **Follow-up contact 2**

The following data will be collected:

- AEs
- Concomitant medication
- Current diabetes medication

### **8.1.9 Premature discontinuation of trial products**

If a subject prematurely discontinues trial products after randomisation (V10), the investigator must undertake procedures as included for V26A as soon as possible (see flowchart Section [2](#)). Subjects who prematurely discontinue trial products during the run-in period before randomisation are considered run-in failures.

Subjects should perform a 7-9-7 point SMPG profile before discontinuing trial products.

Subjects should attend V26A in a fasting state and should undergo the meal test before discontinuing trial products. The meal test should be performed with bolus trial insulin. If it is not feasible due to safety reasons including pregnancy as judged by the investigator the meal test should be performed with the marketed bolus analogue the subject is switched to. The meal test should not be performed if the subject is switched to premix insulin treatment or basal-bolus treatment using regular human insulin as bolus insulin.

In addition, a blood sample for measuring HbA1c must be collected.

The primary reason for premature discontinuation of trial products must be specified in the eCRF, and final drug accountability must be performed. A treatment discontinuation session must be made in the IWRs after the final meal test.

The subject should be switched to a suitable marketed product at the discretion of the investigator.

Protocol  
Trial ID: NN1218-4357  
UTN: U1111-1197-8289

**CONFIDENTIAL**

Date:  
Version:  
Status:  
Page:

30 November 2020  
5.0  
Final  
41 of 105

**Novo Nordisk**

The subject should also complete the follow-up visits (FU1 and FU2) 7 days (+5 days) and 30 days (+ 5 days) after discontinuation of trial product.

Finally, subjects prematurely discontinued from trial products should attend V26B at the time corresponding to 16 weeks after randomisation, where the following assessments will be done:

- Blood sample to measure HbA1c
- SAEs
- Concomitant medication (diabetes)

A subject that permanently discontinues trial product before the End of Treatment visit (V26), will be considered to be a treatment non-completer.

### **8.1.10 Withdrawal from trial**

If a subject withdraws consent, and the subject agrees, the investigator must aim to undertake procedures similar to those for V26A as soon as possible (see flowchart Section 2). The investigator should encourage the subject to undergo the meal test at V26A, which should be done in a fasting state and before trial product is discontinued. The meal test should be performed with bolus trial insulin. If it is not feasible due to safety reasons including pregnancy as judged by the investigator the meal test should be performed with the marketed bolus analogue the subject is switched to. The meal test should not be performed if subject is switched to premix insulin treatment or basal-bolus treatment using regular human insulin as bolus insulin.

If the subject agrees, the follow up visits (FU1 (V27) and FU2 (P28)) must be performed 7 (+5 days) and 30 days (+5 days) after discontinuation of trial product.

The end of treatment and end of trial form in the eCRF must be completed, and final drug accountability must be performed even if the subject is not able to come to the trial site. A treatment discontinuation session must be made in the IWRS. The case book must be signed.

Although a subject is not obliged to give his/her reason(s) for withdrawing consent, the investigator must make a reasonable effort to ascertain the reason(s), while fully respecting the subject's rights. Where the reasons are obtained, the primary reason for withdrawing consent must be specified in the end of-trial-form in the eCRF.

A subject that is withdrawn from trial before the End of Treatment Visit (V26), will be considered to be a treatment non-completer and a trial non-completer.

#### **8.1.10.1 Lost to follow-up**

The following actions must be taken in relation to a subject who fails to attend the site for a required visit:

Protocol  
Trial ID: NN1218-4357  
UTN: U1111-1197-8289

**CONFIDENTIAL**

Date:  
Version:  
Status:  
Page:

30 November 2020  
5.0  
Final  
42 of 105

**Novo Nordisk**

- The site must attempt to contact the subject and reschedule the missed visit as soon as possible
- The site must re-train the subject in the importance of maintaining the scheduled visits

In cases in which the subject is deemed lost to follow-up the investigator must make every effort to regain contact with the subject (e.g. via e-mail or certified letter to the subject as applicable). These contact attempts must be documented in the subject's medical records. Should the subject continue to be unreachable, only then will he/she be considered to have withdrawn from the trial with the primary reason being "lost to follow-up".

